6.6 Criteria for premature discontinuation of trial products

Efforts must be made so that subjects attend and complete all scheduled visit procedures. Subjects should stay in the trial irrespective of lack of adherence to randomised treatment, lack of adherence to visit schedule or missing assessments. Only subjects who decline any further contact with the site in relation to the trial will be considered as withdrawn from the trial (see Section 6.7).

The subject may be prematurely discontinued from trial products at the discretion of the investigator due to a safety concern.

The subject must be prematurely discontinued from trial products if the following applies after randomisation:

- 1. Included in the trial in violation of the inclusion and/or exclusion criteria and/or randomised in violation of the randomisation criterion.
- 2. Pregnancy
- 3. Intention of becoming pregnant
- 4. Simultaneous participation in another clinical trial of an approved or non-approved investigational medicinal product
- 5. Lack of efficacy defined as fulfilment of **all** 4 below criteria:
 - No reduction in HbA_{1c} measured by central laboratory from screening (Visit 1) to visit 18, 22 or 26 AND
 - A daily average of 4-point SMPG readings (before breakfast, before lunch, before dinner and at bed time) on 3 consecutive days higher than 240 mg/dL (13.3 mmol/L) within the last two weeks period AND
 - A confirmatory FPG exceeding 240 mg/dL (13.3 mmol/L) or a confirmatory random PG exceeding 300 mg/dL (16.7 mmol/L) measured by central laboratory AND
 - No treatable intercurrent cause (e.g. non-compliance) for the hyperglycaemia at the investigator's judgment
- 6. Unacceptable adverse event (including toxicity) that cannot be solved by any medical intervention or considered as non-acceptable risk at the investigator's judgment.

Protocol Amendment no 2 Trial ID: NN1218-4113

CONFIDENTIAL

Date: Version: Status: Page:

23 February 2018 | Novo Nordisk Final 1 of 4

Protocol Amendment

no 2

to Protocol, version 3.0 **dated 09 June 2017**

Trial ID: NN1218-4113

Efficacy and Safety of Fast-acting Insulin Aspart Compared to NovoRapid® both in Combination with Insulin Degludec with or without Metformin in Adults with Type 2 Diabetes (onset® 9)

> Trial phase: 3b Applicable to all countries

This confidential document is the property of Novo Nordisk. No unpublished information contained herein may be disclosed without prior written approval from Novo Nordisk. Access to this document must be restricted to relevant parties.

Protocol Amendment no 2 Trial ID: NN1218-4113	CONFIDENTIAL	Date: Version: Status:	23 February 2018 1.0 Final	Novo Nordisi
		Page:	2 of 4	

Table of Contents

1	Introd	luction including rationale for the protocol amendment	3
		ntinuation of the glycaemic data collection system	
2		ges	
-		High-level summary of changes:	
		Primary protocol sections affected	

3 of 4

1 Introduction including rationale for the protocol amendment

Discontinuation of the glycaemic data collection system

Due to an unusual data reporting pattern of hypoglycaemia and glycaemic values in two ongoing randomised clinical trials (NN1250-4252 and NN1218-4113), Novo Nordisk has decided to discontinue the glycaemic data collection system (i.e. the combined use of a BG-meter and eDiary) in trials using this system to protect the safety of the trial participants. This affects the NN1250-4252, NN1218-4113 and NN1250-4300 trials.

This protocol amendment has been created in alignment with the above decision to replace the electronic glycaemic data collection system with a paper diary solution and a new trial BG meter.

2 Changes

The discontinuation of the glycaemic data collection system necessitates update of many sections. Therefore, track-changes version of the protocol, titration guideline and SI-IC serves as documentation of the changes.

2.1 High-level summary of changes:

- Replacement of eDiary requirements with paper diary requirements (in alignment with the protocol template) including change of trial BG-meter. Throughout the protocol "eDiary" has been replaced with "diary"
- Clarification to titration guideline section 3.2. Information was provided to investigators in a memo dated 30-Nov-2017 to make it clear that insulin degludec titration is based on SMPGs two days prior to and on day of contact instead of three days prior to contact
- In agreement with SI-IC SOP author it was decided to include the new statements regarding Personal Data Protection in the amended SI-IC according to updated SI-IC template version 10.0
- Minor clarifying updates to protocol text

2.2 Primary protocol sections affected

- 2 Flowchart
- 8.1.2 Run-in
- 8.1.9 Premature discontinuation of trial products
- 8.1.11 Review of results
- 8.3.2 Discontinuation of MyGlucoHealth BG-meter and eDiary (new section)
- 8.3.3 Self-measured plasma glucose
- 8.3.4 Insulin dose
- 8.4.2 Hypoglycaemic episodes

Protocol Amendment no 2 Trial ID: NN1218-4113	CONFIDENTIAL	Date: Version: Status: Page:	23 February 2018 1.0 Final 4 of 4	Novo Nordisk
--	--------------	---------------------------------------	--	--------------

- 8.6.3 Diary
- 9.5 Auxiliary supplies
- 12.4.1 Reporting of technical complaints
- 12.4.2 Collection, storage and shipment of technical complaint samples
- 13.1 Corrections to case report forms
- 14 Monitoring procedures
- 16 Computerised systems

1.1 Trial information

This is a phase 3b, 16-week, multicentre, multinational, 1:1 randomised, double-blind, active controlled, treat-to-target, parallel group trial with a 12-week run-in period comparing the effect and safety of faster aspart to NovoRapid[®] both in combination with insulin degludec with or without metformin in subjects with T2DM treated with a basal-bolus regimen.

The total duration of the trial is approximately 34 weeks divided into the following periods (see Figure 1–1):

- An approximately 2-week screening period
- A 12-week run-in period primarily for optimisation of the basal insulin and subject training
- A 16-week treatment period
- A 30-day follow-up period: FU1; 7 days after end of treatment and FU2; 30 days after end of treatment

[figure not shown]

Figure 1–1 Trial design

The trial includes a screening period followed by weekly visits/phone contacts during the trial. At Visit 2, all eligible subjects will be enrolled in a 12-week run-in period. After the run-in period, subjects eligible for randomisation (HbA_{1c} \leq 9.0% measured at Visit 13) will be randomised (1:1) to receive double blinded treatment with either faster aspart or NovoRapid[®] both in combination with once daily insulin degludec with or without metformin.

Statistical Analysis Plan		Date:	12 February 2019	Novo Nordisk
Trial ID: NN1218-4113	CONFIDENTIAL	Version:	2.0	
UTN: U1111-1180-0636	CONFIDENTIAL	Status:	Final	
EudraCT No.: 2016-000878-38		Page:	5 of 29	

Subjects will have a standardised meal test at baseline (Visit 14 before randomisation) and at end of treatment (Visit 30). The meal test is described in more detail in section 8.3.1 in the protocol.

After the 16-week treatment period, each subject will have a 30-day safety follow-up period.

The primary objective is to confirm the effect in terms of glycaemic control of treatment with faster aspart compared to NovoRapid® both in combination with insulin degludec with or without metformin in adults with T2DM treated with a basal-bolus regimen, using a non-inferiority approach.

The secondary objectives are to confirm superiority of faster aspart compared to NovoRapid[®] both in combination with insulin degludec with or without metformin in adults with T2D M treated with a basal-bolus regimen in terms of:

- Postprandial glucose regulation
- Overall glycaemic control
- Postprandial glucose excursions

To compare the safety of faster aspart to NovoRapid® both in combination with insulin degludec with or without metformin in adults with T2DM treated with a basal-bolus regimen.

Subjects prematurely discontinued from trial product should continue with the per protocol planned visits at 4 (Visit 18), 8 (Visit 22), 12 (Visit 26), 16 (Visit 30) weeks after randomisation depending on when the subject discontinues trial products.

For further details on handling of subjects that prematurely discontinue from trial product and the trial in general, please see the trial protocol.

1.2 Scope of the statistical analysis plan

This statistical analysis plan (SAP) is based on the protocol *Efficacy and Safety of Fast-acting Insulin Aspart Compared to NovoRapid*[®] *both in Combination with Insulin Degludec with or without Metformin in Adults with Type 2 Diabetes (onset*[®] *9*), version 4.0 (dated 23 February 2018). The statistical analyses and derivations of endpoints presented in this SAP are almost identical to those described in the protocol. It contains minor clarifications for derivations, calculation of endpoints and analyses as well as some additions.

The changes to the statistical considerations proposed in this SAP and the reasons for the changes are described in section $\underline{3}$ and will be reported in the clinical trial report (CTR).

Statistical Analysis Plan Trial ID: NN1218-4113 UTN: U1111-1180-0636 EudraCT No.: 2016-000878-38

CONFIDENTIAL

Date: Version: Status: Page:

12 February 2019 | Novo Nordisk Final 6 of 29

Statistical considerations 2

General considerations

In general, for endpoints evaluated as a change from baseline and/or where a baseline adjustment is made, baseline is defined as information collected at randomisation (Visit 14). In case a measurement is not available at randomisation, the most recent measurement prior to randomisation will be used as baseline.

Two observation periods are defined, "in-trial" and "on-treatment", and it will be specified which period each analysis will use.

- In-trial: The observation period from date of randomisation and until last trial -related subject-site contact. The in-trial observation period includes data collected after treatment discontinuation.
- On-treatment: The observation period from date of first dose of randomised NovoRapid[®]/faster aspart and to 7 days after the first occurrence of:
 - The day of last dose of randomised NovoRapid ®/faster aspart
 - The day before initiation of ancillary treatment

All efficacy endpoints will be summarised and analysed using the full analysis set (FAS), unless otherwise stated. Safety endpoints will be summarised using the safety analysis set and analysed using the FAS, unless otherwise stated. The FAS and safety analysis set are defined in section 2.2.

Presentation of results from a statistical analysis will include the estimated mean treatment effects (LSMeans) for change from baseline, if applicable. Estimated mean treatment differences (or ratios) will be presented together with two-sided 95% confidence interval (CI) for all endpoints analysed statistically.

Data collected before randomisation (Visit 14) will only be summarised descriptively.

Testing strategy and estimands

The primary objective of the trial is to confirm the effect of treatment with faster aspart compared to NovoRapid[®], both in combination with insulin degludec with or without metformin in adults with T2DM in terms of glycaemic control, using a non-inferiority approach.

More specifically the upper limit of the 95% confidence interval for the difference between faster aspart and NovoRapid® should be compared to a non-inferiority margin of 0.4%. If it is below or equal to 0.4% non-inferiority will be considered established and effect demonstrated.

The trial also aims to confirm superiority of treatment with faster aspart for a number of secondary confirmatory endpoints. The family-wise type I error rate will be controlled in the strong sense

 Statistical Analysis Plan
 Date:
 12 February 2019
 Novo Nordisk

 Trial ID: NN1218-4113
 Version:
 2.0

 UTN: U1111-1180-0636
 Status:
 Final

 EudraCT No.: 2016-000878-38
 Page:
 7 of 29

using a hierarchical (fixed sequence) testing procedure under the framework of the primary estimand. This is based on a priority ordering of the null-hypotheses, and testing them in this order using the two-sided 95% confidence interval approach until an insignificant result appears. The effect is that rejection of a null hypothesis only will be considered for analyses where all previous null-hypotheses have been rejected in favour of faster aspart.

The steps in the hierarchical testing procedure are as follows:

- Step 1 (Primary analysis): HbA_{1c} non-inferiority of faster aspart versus NovoRapid[®]
- Step 2: 1-hour PPG increment (meal test) superiority of faster aspart versus NovoRapid®
- Step 3: HbA_{1c} superiority of faster aspart versus NovoRapid®
- **Step 4**: 1,5-anhydroglucitol superiority of faster aspart versus NovoRapid[®]

Primary estimand

The primary estimand is defined as the treatment difference between subjects randomised to faster aspart and NovoRapid[®] both in combination with insulin degludec with or without metformin, in adults with T2DM not optimally controlled with a basal-bolus regimen assessed by change from baseline in HbA_{1c} 16 weeks after randomisation for all randomised subjects regardless of treatment discontinuation or use of ancillary treatment.

The primary estimand assesses the expected benefit a future population with T2DM can achieve if prescribed to faster aspart as compared to NovoRapid[®]. By not putting any restrictions on the treatment adherence, this estimand aims at a difference as close as possible to the one that can be expected in real-world clinical practice, provided that the treatment adherence and use of ancillary treatment reflects clinical practice. Thereby the primary estimand provides a treatment difference for clinicians concerning the glycaemic effect of faster aspart compared to NovoRapid[®] in the day to day life in subjects with T2DM in an adult population.

Secondary estimand

A secondary estimand is defined as the treatment difference in change from baseline in HbA_{1c} 16 weeks after randomisation between treatment with faster aspart and treatment with NovoRapid both in combination with insulin degludec with or without metformin in adult subjects with T2DM not optimally controlled with a basal-bolus regimen if all subjects had adhered to randomised treatment and did not receive ancillary treatment.

The condition 'adhered to randomised treatment and did not receive ancillary treatment' should be interpreted as the exclusion of information collected after initiation of antidiabetic treatment that can mask or exaggerate the effect of the initially randomised treatment. Only data collected prior to

discontinuation of trial product or initiation of ancillary treatment is used to draw inference. This avoids confounding effects of ancillary treatment.

The two estimands will be repeated for the confirmatory endpoints

- Change from baseline in 1-hour PPG increment (meal test) 16 weeks after randomisation
- Change from baseline in 1,5-anhydroglucitol 16 weeks after randomisation

Visit reallocation

Subjects that prematurely discontinue from treatment or withdraw from trial will attend end of treatment visit called visit 30A. Data collected at this visit will be reallocated to the next scheduled visit where the given assessment is planned. As a general rule, all observed values from randomised subjects will be used in all statistical analyses, but in case two different values are associated to the same visit in time, the use of a given value will depend on the estimand of interest. For the primary estimand the reallocated on-treatment value will not be used and for the secondary estimand the reallocated on-treatment value will be used.

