8.1.9 Premature discontinuation of trial products

If a subject prematurely discontinues trial products after randomisation (Visit 14), the investigator must undertake procedures similar to those for Visit 30 as soon as possible, also called Visit 30A (see flowchart section 2).

Premature discontinuation of trial products must be registered in IWRS. This must be performed at least 4 days prior to Visit 30A to ensure scheduling of the 7-9-7-point SMPG profile on the three days prior to Visit 30A. Subjects should perform this 7-9-7 point SMPG profile before discontinuing trial products.

At Visit 30A subjects must undergo the meal test before discontinuing trial products. The meal test should be performed with bolus trial insulin. If it is not feasible due to safety reasons including pregnancy as judged by the investigator the meal test should be performed with the marketed bolus product the subject is switched to.

The primary reason for premature discontinuation of trial products must be specified in the eCRF, and final drug accountability must be performed. A treatment discontinuation session must be made in the IWRS after the final meal test.

Protocol		Date:	23 February 2018	Novo Nordisk
Trial ID: NN1218-4113	CONFIDENTIAL	Version:	4.0	
UTN: U1111-1180-0636	CONFIDENTIAL	Status:	Final	
EudraCT no.: 2016-000878-38		Page:	36 of 112	

The subject should be switched to a suitable marketed product at the discretion of the investigator. The medication should be recorded on the concomitant medication (diabetes) form in the eCRF, as described in section 8.2.6 at each contact after trial product discontinuation.

The subject should also complete the follow-up visits (FU1 and FU2) 7 days and 30 days after discontinuation of trial product. Visit 31 (FU1) can be converted into a phone contact as the diary can be collected at the next site visit for the subjects that discontinue trial products prematurely.

In addition, subjects prematurely discontinued from trial products should continue with the per protocol planned visits at 4 (Visit 18), 8 (Visit 22), 12 (Visit 26), 16 (Visit 30) weeks after randomisation depending on when the subject discontinues trial products. The meal test at Visit 30 should be done with the subjects' currently prescribed insulin treatment with the same bolus insulin dose as at baseline.

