 23 February 2018
 Novo Nordisk

 Trial ID: NN1218-4113
 Version:
 4.0

 UTN: U1111-1180-0636
 Status:
 Final

Page:

79 of 112

not optimally controlled with a basal-bolus regimen if all subjects had adhered to randomised treatment and did not receive ancillary treatment.

The condition 'adhered to randomised treatment and did not receive ancillary treatment' should be interpreted as the exclusion of information collected after initiation of antidiabetic treatment that can mask or exaggerate the effect of the initially randomised treatment. Only data collected prior to discontinuation of trial product or initiation of ancillary treatment is used to draw inference. This avoids confounding effects of ancillary treatment.

The two estimands will be repeated for the confirmatory endpoints

- Change from baseline in 1-hour PPG increment (meal test) 16 weeks after randomisation
- Change from baseline in 1,5-anhydroglucitol 16 weeks after randomisation

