- d) A tipping point analysis based on a statistical model using multiple imputations similar to 1), using the in-trial observation period, will be made. In this analysis, observations for subjects without a measurement are imputed based on the treatment arm they were randomised to and subjects on faster aspart without a measurement are given a penalty. This is done to investigate the robustness of the conclusion in the primary analysis with respect to the MAR assumption and mimics a scenario where the HbA_{1c} of the subjects without a measurement in the faster aspart group evolve less favourably than predicted. As a first step imputations will be done without penalty assuming MAR in the treatment group. Second, the imputed values for week 16 in the faster aspart group will be added a penalty. This is done repeatedly, gradually increasing the penalty until the conclusion from the non-inferiority analysis no longer holds. This will serve as a sensitivity analysis for the noninferiority analysis and the specific value of the penalty that changes the conclusion will be used to evaluate the robustness of the conclusion of the non-inferiority analysis.

Analyses addressing the secondary estimand

All analyses addressing the secondary estimand will use the on-treatment observation period.

- 4) The secondary estimand will be analysed using the same statistical model using multiple imputations as the primary analysis in 1) except using the on-treatment observation period.
- 5) A tipping point analysis based on a statistical model using multiple imputations, similar to sensitivity analysis 3)-d except using the on-treatment observation period.
- 6) A tipping point analysis based on a statistical model using multiple imputation, similar to 5) but with the modification that subjects without a measurement that discontinued treatment due to non-eligibility (Subjects discontinuing randomised treatment prematurely due to criteria 1, 2, 3, and 4, which are defined in section 6.6 in the protocol) in the faster aspart

group will not have a penalty added to the imputed values. This analysis is motivated by the fact that data from subjects prematurely discontinuing randomised treatment due to non-eligibility can reasonably be assumed to be missing completely at random.

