2.4 Secondary endpoints

2.4.1 Confirmatory secondary endpoints

If the effect of treatment with faster aspart can be confirmed in the primary analysis, the trial also aims to confirm effect of treatment with faster aspart for a number of secondary confirmatory endpoints using a hierarchical (fixed sequence) testing procedure as described in section 2 (General consideration). This is based on a priority ordering of the null-hypotheses, and testing them in this order using the two-sided 95% confidence interval approach until an insignificant result appears. The effect is that rejection of the null hypothesis will only be confirmed for endpoints where all previous null-hypotheses have been rejected in favour of faster aspart.

The confirmatory secondary endpoints are:

- Change from baseline in 1-hour PPG increment 16 weeks after randomisation (meal test)
- Change from baseline in 1,5-anhydroglucitol 16 weeks after randomisation

The steps in the hierarchical testing procedure are as follows:

- Step 1 (Primary analysis): HbA_{1c} non-inferiority of faster aspart versus NovoRapid[®]
- Step 2: 1-hour PPG increment (meal test) superiority of faster aspart versus NovoRapid®
- **Step 3:** HbA_{1c} superiority of faster aspart versus NovoRapid[®]
- Step 4: 1,5-anhydroglucitol superiority of faster aspart versus NovoRapid®

The primary estimand for the primary endpoint will be repeated for the confirmatory secondary endpoints, change from baseline in 1-hour PPG increment (meal test) and change from baseline in 1,5-anhydroglucitol 16 weeks after randomisation. The analyses related to these estimands are defined below and will be used for the decisions to continue or not, throughout the hierarchical testing procedure. These analyses will be based on the FAS and use the in-trial observation period.

Statistical Analysis Plan		Date:	12 February 2019	Novo Nordisk
Trial ID: NN1218-4113	CONFIDENTIAL	Version:	2.0	
UTN: U1111-1180-0636	CONFIDENTIAL	Status:	Final	
EudraCT No.: 2016-000878-38		Page:	16 of 29	

As sensitivity analysis the secondary analysis 4) will also be repeated for the confirmatory secondary endpoints. The analyses will be based on the FAS and using the on-treatment observation period.

Change from baseline in 1-hour PPG increment 16 weeks after randomisation (meal test) (step 2)

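### The secondary estimand admits only data from before discontinuation, but its on-treatment period runs 7 days longer and can take in a Visit 30A meal test dosed with a marketed bolus insulin

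*SAP*

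**What the plan says.** The data rule for the secondary estimand is in Protocol v4.0 section 17 (Secondary estimand): "Only data collected prior to discontinuation of trial product or initiation of ancillary treatment is used to draw inference". The SAP keeps it under the same heading, limiting inference to data from before the point where "discontinuation of trial product or initiation of ancillary treatment is used to draw inference". The estimand is written for HbA1c and repeated for the 1-hour PPG increment and 1,5-anhydroglucitol.

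The observation period is defined in SAP section 2, General considerations, and identically in Protocol section 17. On-treatment runs from first dose of randomised NovoRapid or faster "aspart and to 7 days after the first occurrence of" two events: the day of the last randomised bolus dose, or "The day before initiation of ancillary treatment". One definition serves all efficacy endpoints.

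SAP section 2.3 links the two: "All analyses addressing the secondary estimand will use the on-treatment observation period". SAP section 2.4.1 carries this to the meal test: "As sensitivity analysis the secondary analysis 4) will also be repeated for the confirmatory" secondary endpoints. SAP section 2.4.2.1 repeats the supportive efficacy endpoints, except insulin dose, on-treatment as well.

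Protocol section 8.1.9 requires the Visit 30A meal test before trial product is stopped, with bolus trial insulin. If that is not feasible for safety reasons, including pregnancy, "the meal test should be performed with the marketed bolus product the subject is switched to". Section 8.1.10 gives the same exception for subjects withdrawing consent. Under Visit reallocation, the SAP moves Visit 30A data to the next visit at which the assessment is planned. Where two values then compete for one visit, "for the secondary estimand the reallocated on-treatment value will be used".

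**The concern.** The wording of the estimand allows no days after discontinuation; the data set built for it allows seven. For HbA1c this hardly matters, because Protocol section 3.2 treats it as a measure of long-term control. A meal test is different: it reflects the insulin injected minutes earlier. If that insulin is a marketed product and the value is still labelled on-treatment, a result from non-randomised treatment is analysed as the result under adherence.

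At stake is the meaning of the on-treatment analysis named as the sensitivity analysis for the 1-hour PPG increment, and of the supportive meal-test repeats. A reader should be able to say which insulin produced the values in them.

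**Working it through.** **1. The two rules side by side.**
- After discontinuation: the estimand sentence allows 0 days; the on-treatment period allows 7.
- After ancillary treatment starts (day 0): the estimand sentence allows 0 days. The period's anchor is day -1, so it ends on day -1 + 7 = 6.

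Nothing in either document reconciles them. SAP section 3 says that Visit 30A handling was clarified, but the gap remains.

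**2. Can a marketed-insulin meal test fall inside the window?** Protocol section 8.1.9 asks for discontinuation to be registered at least 4 days before Visit 30A. Assume an abrupt stop, registered on the day of the last dose (day 0).
- Earliest Visit 30A, with its meal test: day 0 + 4 = day 4.
- SMPG profile on the three preceding days: days 1-3.
- Window closes: day 7.

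A Visit 30A on days 4-7 therefore counts as on-treatment. The only later planned meal test is Visit 30, so the value goes to week 16.

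The Visit 30 meal test itself does not enter this way if the rules are followed. When Visit 30A is within 2 weeks of Visit 30, only Visit 30A is done; otherwise Visit 30 is more than 7 days after the last dose.

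**3. The plan's own figure for this endpoint.** SAP section 2.1 gives a difference of 0.6 mmol/L, SD 3.5 mmol/L, 536 per arm and a two-sided 5% t-test.
- Standard error = 3.5 × √(2/536) = 0.214.
- Noncentrality = 0.6 / 0.214 = 2.81, with 1070 degrees of freedom.
- Power = 80.06%, which reproduces the stated 80.1%.

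**4. Ceiling on the numbers affected.** SAP section 2.1 expects about 10% treatment discontinuation, half of it also trial discontinuation.
- All discontinuers: 0.10 × 1072 = 107, or about 54 per arm.
- Discontinuers who stay in the trial: about 27 per arm, which is 5% of 536.

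The share f with a marketed-insulin meal test inside the window is not given. It should be well below these ceilings, since it requires both the safety exception and the right timing.

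**5. Illustrative dilution.** Assume that a share f of each arm has such a value and that those values carry no between-arm difference. Then the diluted difference = 0.6 × (1 - f).

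| f | Affected per arm | Difference (mmol/L) | Shift | Shift / SE |
|---|---|---|---|---|
| 1% | 5.4 | 0.594 | 0.006 | 0.03 |
| 5% | 26.8 | 0.570 | 0.030 | 0.14 |

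At the planned size and SD, a test of 0.594 would have 79.3% power and a test of 0.570 would have 75.9%. These only show scale for the on-treatment analysis; no power figure in the plan changes.

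**The case against.** The best defence is that programming is not in doubt. SAP section 2.3 names the period, one definition is applied across efficacy endpoints, and it is worded the same in protocol and SAP. That is true, but it does not make the estimand sentence agree with the data used. The plan also already varies its windows by outcome: SAP section 2.4.2.2 allows 7 days for adverse events but one day for hypoglycaemia.

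Several limits stand in full. Trial insulin is the default at Visit 30A, so the marketed-insulin test is an exception within an exception. The shift is at most about a seventh of a standard error at an extreme assumed share. Simply dropping the values is not enough either: the supportive meal-test endpoints use the Step 2 model, which imputes both arms from NovoRapid, so excluded faster aspart values would there be replaced by NovoRapid-like ones.

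Four stronger readings may tempt a reader, and the documents support none of them.
- *The confirmatory Step 2 test is biased.* SAP sections 2 and 2.4.1 place the testing hierarchy under the primary estimand with in-trial data.
- *The difference is certainly pulled towards zero.* The protocol says only that the replacement is a suitable marketed product. It could be NovoRapid or marketed faster aspart, so a subject might even be tested on the randomised substance.
- *SMPG profiles are misclassified in the same way.* Protocol section 8.1.9 says the profile should be done before stopping. Post-switch readings arise only after an abrupt stop, and they enter through the supportive on-treatment repeats because the secondary estimand does not cover SMPG.
- *The insulin product used in the meal test is already recorded.* Protocol section 8.3.1 lists the time and dose of the bolus but not the product.

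**Conclusion.** The inconsistency between the estimand wording and the on-treatment period is real and present in both documents. Under the stated rules it has one clear consequence: a Visit 30A meal test on a marketed bolus product, within 7 days of the last randomised dose, is used as the week-16 value under adherence.

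The consequence is small. With an assumed 1-5% affected and no between-arm difference among them, the on-treatment Step 2 difference would move from 0.6 to 0.594-0.570 mmol/L. Both assumptions are illustrative; neither the share nor the contrast is in the documents. Dilution towards no difference is likely but not certain. The confirmatory tests, type I error, sample size and stated power are unaffected. This is a minor correction, worth making because it is cheap and settles what the sensitivity analysis contains.

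**What to change.** In the SAP:

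1. For secondary-estimand and on-treatment meal-test analyses, use only meal tests dosed with the randomised bolus insulin: on or before the last randomised dose and before any ancillary treatment. Derive this from the last-dose date, the start dates on the diabetes-medication form (Protocol section 8.2.6) and the recorded meal-test injection time.
2. Apply the same date cut to SMPG values in the on-treatment repeats.
3. State that excluded values in the Step 2 sensitivity analysis are imputed from the subject's own randomised arm, as in analysis 4. For the supportive meal-test repeats, say which imputation applies, since the Step 2 model would draw on NovoRapid.
4. Reword the secondary-estimand sentence so that it agrees with the 7-day window wherever that is kept (HbA1c and 1,5-anhydroglucitol).

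The cost is a few sentences and one derived flag from dates already collected. The downside is that a few more values are imputed.
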